8.3. Adverse Events and Serious Adverse Events

The definitions of an AE and an SAE can be found in [Appendix 3](#).

AEs will be reported by the participant (or, when appropriate, by a caregiver, surrogate, or the participant's legally authorized representative).

The investigator and any qualified designees are responsible for detecting, documenting, and recording events that meet the definition of an AE or SAE and remain responsible to pursue and obtain adequate information both to determine the outcome and to assess whether it meets the criteria for classification as an SAE or that caused the participant to discontinue the PF-06826647 (see [Section 7](#)).

In addition, the investigator may be requested by Pfizer Safety to obtain specific follow-up information in an expedited fashion.

8.3.1. Time Period and Frequency for Collecting AE and SAE Information

The time period for actively eliciting and collecting AEs and SAEs (“active collection period”) for each participant begins from the time the participant provides informed consent, which is obtained before the participant’s participation in the study (ie, before undergoing any study-related procedure and/or receiving investigational product), through and including a minimum of 28 calendar days, except as indicated below, after the last administration of the investigational product.

For participants who are screen failures, the active collection period ends when screen failure status is determined.

Medical occurrences that begin before the start of study intervention but after obtaining informed consent will be recorded on the Medical History/Current Medical Conditions section of the case report form (CRF), not the AE section.

Follow-up by the investigator continues throughout and after the active collection period and until the event or its sequelae resolve or stabilize at a level acceptable to the investigator, and Pfizer concurs with that assessment.

Investigators are not obligated to actively seek AEs or SAEs after conclusion of the study participation. However, if the investigator learns of any SAE, including a death, at any time after a participant has been discharged from the study, and he/she considers the event to be reasonably related to the study intervention or study participation, the investigator must promptly notify the sponsor.

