1.2. Schema

1.3. Schedule of Activities (SoA)

The SoA table provides an overview of the protocol visits and procedures. Refer to the [STUDY ASSESSMENTS AND PROCEDURES](#) section of the protocol for detailed information on each procedure and assessment required for compliance with the protocol.

The investigator may schedule visits (unplanned visits) in addition to those listed in the SoA table, in order to conduct evaluations or assessments required to protect the well-being of the participant

Study Procedure	Screening	Baseline	Investigational Treatment Period							Extension Treatment Period		Follow-Up ^b	Early Termination ^c
			1	2	4	6	8	12	16	18/20/24/28/32/36	40		
Visit Identifier (Week)	-6 to -1	0	1	2	4	6	8	12	16	18/20/24/28/32/36	40	20 or 44	
Study Day ^a	-42 to -1	1	8	15	29	43	57	85	113	127/141/169/197/225/253	281	141 or 309	
Visit Window (Days)	N/A		±1	±1	±2	±2	±2	±2	±2	±3	±3	±3	
Enrollment Procedures													
Informed consent	X												
Medical history & demography	X												
Eligibility assessment	X	X											
Medication History	X												
Randomization		X											
Clinical Assessments													
Full Physical Exam	X	X							X		X		X
Brief Physical Exam			X	X	X	X	X	X		X		X	
Vital signs ^d	X	X	X	X	X	X	X	X	X	X	X	X	X
ECG ^d	X	X			X				X		X		X
Height/Weight ^e	X	X							X		X		
Chest radiograph ^f	X												
C-SSRS ^g	X	X							X		X		
Laboratory Assessments													
Hematology/Blood chemistry	X	X	X	X	X	X	X	X	X	X	X	X	X
Lipid panel ^h (fasting)		X			X				X		X		
Urinalysis ⁱ	X	X			X				X		X		
FSH ^j	X												
Serum β-HCG ^k	X												

Study Procedure	Screening	Baseline	Investigational Treatment Period							Extension Treatment Period		Follow-Up ^b	Early Termination ^c
			1	2	4	6	8	12	16	18/20/24/28/32/36	40		
Visit Identifier (Week)	-6 to -1	0	1	2	4	6	8	12	16	18/20/24/28/32/36	40	20 or 44	
Study Day ^a	-42 to -1	1	8	15	29	43	57	85	113	127/141/169/197/225/253	281	141 or 309	
Visit Window (Days)	N/A		±1	±1	±2	±2	±2	±2	±2	±3	±3	±3	
Urine β-HCG ^l (done at site)		X	X	X	X	X	X	X	X	X	X	X	X
HIV serology/HBsAg, HBcAb, (HepB reflex testing), and HCVAb ^m	X												
Tuberculosis test ⁿ	X												
CCI [REDACTED]													
CCI [REDACTED]													
Study treatment													
IP dispensing ^q		X	X	X	X	X	X	X	X	X	X		
IP accountability			X	X	X	X	X	X	X	X	X	X	X
Dosing diary ^r			X	X	X	X	X	X	X	X	X	X	X
Clinical Assessments of psoriasis													
PASI, CCI PGA	X	X	X	X	X	X	X	X	X	X	X	X	X
PROs ^s													

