- Chest X-ray or other appropriate chest diagnostic imaging (ie, CT or MRI) may be performed within 12 weeks prior to Day 1.
- Use C-SSRS “Lifetime” version at Screening and Baseline and “Since Last Visit” version at visits indicated in SoA. Participants who have recent or active suicidal ideation or behaviors will be excluded from study entry or after Day 1, would be discontinued from treatment and referred to a mental health professional for appropriate evaluation and treatment.
- Participants must be fasting (water only) for at least 8 hours prior to visits, when lipid panel is being assessed.
- Dipstick in all cases; microscopy analysis is indicated if urinalysis is positive for blood, nitrite, leukocyte esterase and/or protein. Urine culture is performed if urinalysis is positive for nitrite and/or leukocyte esterase or if clinically indicated.

- j. To be done in females (<60 years of age) who are amenorrheic for at least 12 consecutive months.
- k. Required for WOCBP at Screening
- l. Required for WOCBP prior to dosing at baseline and at all subsequent visits. To be conducted at the site. Pregnancy tests (serum or urine) may also be repeated more frequently as per request of IRBs/ECs or if required by local regulations.
- m. HepB reflex testing only if HBsAg negative but HBcAb positive at Screening. If result of HCVAb is positive, or if Hepatitis C Virus (HCV) antibody result is indeterminate, then a HCV RNA AMPLIPREP TAQMAN 2.0 will automatically be performed. In Japan see [Section 5.1](#) for HBV and HCV details.
- n. If not performed within 12 weeks prior to Screening (see Assessments [Section 8.2.1.1](#) for details).
- o. PK samples will be collected per [SoA](#) prior to dosing, and at 0.5 hour (± 5 min); at 1 and 2 hours (± 10 min) and 4 hours (± 20 min) post dose hours.
- C** [REDACTED]
- q. Participants should take blinded study medication daily during the Investigational Treatment Period and Extension Period; however, on study visit days, participants are instructed to refrain from dosing at home, and are to take the dose in the clinic.
- r. Participants will be reminded to complete the dosing diary daily throughout the study.
- s. All procedures should be performed before dosing of IP. Effort should be made to complete all PRO questionnaires before any other assessments except at Baseline when eligibility needs to be confirmed.

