Participants who request to discontinue receipt of study treatment will remain in the study and proceed to ET visit as soon as possible. Whenever possible, these participants should have one visit approximately two weeks after the last dose (Week 20 or 44 Follow up visit assessments) and/or at least 28 days after the last dose of IP was administered.

The only exception to this is when a participant specifically withdraws consent for any further contact with him or her or persons previously authorized by the participant to provide this information. Participants should notify the investigator in writing of the decision to withdraw consent from future follow-up, whenever possible. The withdrawal of consent should be explained in detail in the medical records by the investigator, as to whether the withdrawal is only from further receipt of investigational product or also from study procedures and/or posttreatment study follow-up, and entered on the appropriate CRF page. In the event that vital status (whether the participant is alive or dead) is being measured, publicly available information should be used to determine vital status only as appropriately directed in accordance with local law.

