8.3.1.1. Reporting SAEs to Pfizer Safety

All SAEs occurring in a participant during the active collection period are reported to Pfizer Safety on the CT SAE Report Form immediately and under no circumstance should this exceed 24 hours, as indicated in [Appendix 3](#). The investigator will submit any updated SAE data to the sponsor within 24 hours of it being available.

SAEs occurring in a participant after the active collection period has ended are reported to Pfizer Safety if the investigator becomes aware of them; at a minimum, all SAEs that the investigator believes have at least a reasonable possibility of being related to investigational product must be reported to Pfizer Safety.

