8.3.5.1. Exposure During Pregnancy

Details of all pregnancies in female participants and, if indicated, female partners of male participants will be collected after the start of study intervention and until at least 5 terminal half-lives or approximately 7 to 11 days after the last dose.

If a pregnancy is reported, the investigator should inform the sponsor within [24 hours] of learning of the pregnancy and should follow the procedures outlined in [Appendix 4](#).

Abnormal pregnancy outcomes (eg, spontaneous abortion, fetal death, stillbirth, congenital anomalies, ectopic pregnancy) are considered SAEs.

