Appendix 2. Data Derivation Details

Appendix 2.1. Definition and Use of Visit Windows in Reporting

Visit windows will be used for efficacy variables, and for any safety data that display or summarize by study visit.

Visit No.	Visit Label	Target Day	Visit Window ^d
1	Screening	N/A	$-42 \leq \text{day} \leq -1$
2	Baseline ^a	1	day = 1
3	Week 1	8	$2 \leq \text{day} \leq 11$
4	Week 2	15	$12 \leq \text{day} \leq 21$
5	Week 4	29	$22 \leq \text{day} \leq 35$
6	Week 6	43	$36 \leq \text{day} \leq 49$
7	Week 8	57	$50 \leq \text{day} \leq 70$
8	Week 12	85	$71 \leq \text{day} \leq 98$
9	Week 16 ^b	118	$99 \leq \text{day} \leq \text{MIN} (129, \text{first dosing day at Week 18} - 1)$
10	Week 18 ^b	127	$\text{MIN} (129, \text{first dosing day at Week 18} - 1) + 1 \leq \text{day} \leq 133$
11	Week 20	141	$134 \leq \text{day} \leq 154$
12	Week 24	169	$155 \leq \text{day} \leq 182$
13	Week 28	197	$183 \leq \text{day} \leq 210$
14	Week 32	225	$211 \leq \text{day} \leq 238$
15	Week 36	253	$239 \leq \text{day} \leq 266$
16	Week 40 ^c	281	$267 \leq \text{day} \leq 305$

a. Baseline analysis visit window may be considered as day ≤ 1 in some analyses (eg, those involving change from baseline). That is, in case that Day 1 observation is missing, the last observation by the first dosing date may be considered as the baseline. The baseline measurements for demography, height, pre-study medical history and medications will be collected at the “Screening” visit.
 
b. If the nominal week 16 assessments happened at the same day as Week 18 dosing, for all the efficacy and safety endpoints analyses by visit, that day will be counted as Week 16 visit, but for the dosing and compliance analysis, that day will be counted as Week 18 visit.
 
c. For the last on treatment visit of Week 40, we extended the visit window to include more data collected in the study. And here day 305 is the day before the scheduled target day of follow-up visit (309\pm3).
 
d. For multiple observations fall into a same window, following algorithm will be taken to identify the observation for analysis:
 
 1. The observation closest to the targeted day will be used. 2. If the observations are with equal distant from the targeted day in absolute value, the one after the targeted day will be used. 
All observations will, however, be included in the listings.
			

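### Minor: for participants who complete Week 16 (without the Extension) or Week 40, an in-window Follow-Up visit can fall before the 28-day minimum for active AE/SAE collection

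*Protocol*

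**What the plan says.** Protocol 8.3.1 runs active AE/SAE collection from consent "through and including a minimum of 28 calendar days, except as indicated below, after the last administration of the investigational product". The exception that follows is: "For participants who are screen failures, the active collection period ends when screen failure status is determined". No dosed participant is exempt.

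The SoA (Protocol 1.3) counts study days from Day 1. Week 16 is Day 113 ±2, Week 40 is Day 281 ±3, and Follow-Up is Day 141 (no Extension) or Day 309 (after the Extension), ±3. AE monitoring is marked at Follow-Up and no contact is scheduled after it. Footnote q says that "on study visit days, participants are instructed to refrain from dosing at home, and are to take the dose in the clinic", so the last dose can fall on the last on-treatment visit day.

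Two provisions leave room for a later contact. The SoA introduction says: "The investigator may schedule visits (unplanned visits) in addition to those listed in the SoA table". Section 7.2 asks for a visit "at least 28 days after the last dose of IP was administered", but only for participants who ask to stop treatment, and as one alternative in an and/or with a visit at about two weeks. Section 4.4 treats a participant as complete at the last visit or scheduled procedure in the SoA. Section 8.3.1 adds that, once participation has concluded, investigators have no duty to look for AEs actively.

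**The concern.** The minimum in 8.3.1 runs from the last dose, while the visit that would deliver it is scheduled from Day 1. Because the two targets are exactly 28 days apart, any Follow-Up held early, or any last on-treatment visit held late, uses up days that the minimum does not have. The site commits no visit deviation, yet may have asked about AEs for the last time before day 28.

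Safety is the primary objective of the Extension, and Follow-Up is its last scheduled AE contact. At stake is the completeness of late AE ascertainment over a few days. The PASI 90 comparison, its error rate and its power are not involved.

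**Working it through.** **The plan's own figures.** 309 − 281 = 28 days and 141 − 113 = 28 days, which matches the stated Follow-Up four weeks after treatment. The total also reproduces: 6 + 16 + 24 + 4 = 50 weeks.

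**Formula.** Gap from last dose to Follow-Up = 28 + f − w + k, where
- f = Follow-Up offset from target, −3 to +3 (SoA);
- w = last on-treatment visit offset, −3 to +3 for Week 40 or −2 to +2 for Week 16 (SoA);
- k = 0 if the last dose is on the visit day (footnote q), 1 if it is the day before.

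**Results.**

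| Last visit | Last dose | Gap, visit on target (w = 0) | Permitted days short of 28 | Smallest gap (visit late, Follow-Up early) |
|---|---|---|---|---|
| Week 40 | visit day | 25 to 31 | 3 of 7 | 306 − 284 = 22 |
| Week 40 | day before | 26 to 32 | 2 of 7 | 306 − 283 = 23 |
| Week 16 | visit day | 25 to 31 | 3 of 7 | 138 − 115 = 23 |
| Week 16 | day before | 26 to 32 | 2 of 7 | 138 − 114 = 24 |

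The largest shortfalls are 28 − 22 = 6 days and 28 − 23 = 5 days. With visit-day dosing, 21 of the 49 in-window day pairs for Week 40 and 15 of the 35 for Week 16 give fewer than 28 days. With day-before dosing the counts are 15 of 49 and 10 of 35. These count combinations and are not probabilities.

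**Distance from exposure.** Section 8.3.5.1 collects pregnancies "until at least 5 terminal half-lives or approximately 7 to 11 days after the last dose". Taking 11 days as the upper figure for 5 half-lives, the exposed days begin at least 25 − 11 = 14 days later with the last visit on target, and 22 − 11 = 11 days later at the extreme.

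**Would a one-sided window alone be enough?** No. With 0/+3 still counted from Day 1, the gap can be 309 − 284 = 25 days or 141 − 115 = 26 days. The anchor has to move to the last dose.

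**Check of the proposed window for completers.** The start is last dose + 28 and the window runs 3 days. Week 40 completers also have a floor at Day 306.
- Week 40, dosed on the visit day (Days 278 to 284): Follow-Up on Days 306 to 315.
- Week 40, last dose the day before (Days 277 to 283): without a floor, the earliest day is 277 + 28 = 305, the last day of the SAP Week 40 window (Days 267 to 305). With the floor, Days 306 to 314.
- Week 16, dosed on the visit day (Days 111 to 115): Days 139 to 146.
- Week 16, last dose the day before (Days 110 to 114): Days 138 to 145. The SAP Week 16 window ends by Day 129, so these completers need no floor.

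The minimum gap is 28 days in all four cases.

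**The case against.** The strongest reply is that no requirement is missing. The 28-day minimum is binding, 8.3.1 does not say that Follow-Up closes the collection period, and the site may add an unplanned visit. On that view a site falls short only by ignoring 8.3.1. This stands to the extent that the two texts do not contradict each other. A reader might infer a contradiction, and the documents do not support one. The gap remains, however. No later contact is scheduled, 4.4 lets participation end at Follow-Up, and the sentence in 8.3.1 on concluded participation gives a site that saw the participant on Day 306 a reasonable ground for stopping.

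A second reply is that visit-day dosing is the less favourable case. Forty weeks are 280 days, so planned dosing could end on Day 280. SAP Appendix 2.1, footnote b, also counts a combined Week 16 assessment and Week 18 dosing day as Week 18 for dosing. The documents do not settle which case applies. Day-before dosing narrows the shortfall but does not remove it.

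A third reply is that no result is shown to change. This stands. The SAP defines a treatment-emergent AE with a lag time whose value is not given in the visible text, so it is not shown that events on the exposed days would enter any table. A reader might also infer that SAEs are lost or that arms are treated differently. Neither follows: "SAEs occurring in a participant after the active collection period has ended are reported to Pfizer Safety if the investigator becomes aware of them", and the windows are the same in every arm.

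**Conclusion.** The concern holds as a minor scheduling gap for participants who complete Week 16 without entering the Extension, or who complete Week 40. A fully in-window schedule permits the last AE assessment 1 to 3 days early when the last visit is on target and dosed that day, or 1 to 2 days early if the last dose was the day before. At the window extremes with visit-day dosing it can be up to 6 days early (Week 40) or 5 days early (Week 16).

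This rests on the SoA days and windows as printed, on a last dose on the visit day or the day before, and on sites making no unscheduled contact after Follow-Up. How often such gaps would occur cannot be derived from the documents, so 3 of 7 should not be read as a rate. The consequence is limited to a few days of eliciting mainly non-serious AEs, well after 5 half-lives. It is worth correcting because the change is nearly free and makes the schedule deliver the protocol's own minimum.

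**What to change.** In the SoA Follow-Up column or footnote b, for participants who complete Week 16 (without the Extension) or Week 40, schedule Follow-Up at least 28 days after the actual last dose, with a one-sided window (for example −0/+3 days). For Week 40 completers, add that it is not before Day 306; if last dose + 28 is earlier, the window starts on Day 306. This keeps Follow-Up outside the SAP Week 40 window. Footnote c of SAP Appendix 2.1 places that boundary where "here day 305 is the day before the scheduled target day of follow-up visit" (309 ± 3), so the SAP can stay as it is.

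Limit the change to completers. Early stoppers keep the Early Termination and follow-up timing in 7.1 and 7.2. A Day 306 floor for them would conflict with 7.2: a last dose on Day 170 would mean waiting 306 − 170 = 136 days. Nor does the absence of a floor outside the Extension carry over to them. A last dose on Days 71 to 101 puts last dose + 28 on Days 99 to 129, which can fall inside the SAP Week 16 window, and PASI is collected at Follow-Up.

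The cost is one footnote. The latest Follow-Up moves from Day 312 to 315, or from Day 144 to 146. The example window has 4 days instead of 7 and could be widened on the late side. A sponsor that prefers not to move the visit could instead schedule a contact on or after day 28 from the last dose.

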8.3.1.1. Reporting SAEs to Pfizer Safety

All SAEs occurring in a participant during the active collection period are reported to Pfizer Safety on the CT SAE Report Form immediately and under no circumstance should this exceed 24 hours, as indicated in [Appendix 3](#). The investigator will submit any updated SAE data to the sponsor within 24 hours of it being available.

SAEs occurring in a participant after the active collection period has ended are reported to Pfizer Safety if the investigator becomes aware of them; at a minimum, all SAEs that the investigator believes have at least a reasonable possibility of being related to investigational product must be reported to Pfizer Safety.

8.3.1.2. Recording Nonserious AEs and SAEs on the CRF

During the active collection period, both nonserious AEs and SAEs are recorded on the CRF.

8.3.2. Method of Detecting AEs and SAEs

The method of recording, evaluating, and assessing causality of AEs and SAEs and the procedures for completing and transmitting SAE reports are provided in [Appendix 3](#).

Care will be taken not to introduce bias when detecting AEs and/or SAEs. Open-ended and nonleading verbal questioning of the participant is the preferred method to inquire about AE occurrences.

8.3.3. Follow-up of AEs and SAEs

After the initial AE/SAE report, the investigator is required to proactively follow each participant at subsequent visits/contacts. For each event, the investigator must pursue and obtain adequate information until resolution, stabilization, the event is otherwise explained, or the participant is lost to follow-up (as defined in [Section 7.3](#)).

In general, follow-up information will include a description of the event in sufficient detail to allow for a complete medical assessment of the case and independent determination of possible causality. Any information relevant to the event, such as concomitant medications and illnesses, must be provided. In the case of a participant death, a summary of available autopsy findings must be submitted as soon as possible to Pfizer Safety.

Further information on follow-up procedures is given in [Appendix 3](#).

8.3.4. Regulatory Reporting Requirements for SAEs

Prompt notification by the investigator to the sponsor of an SAE is essential so that legal obligations and ethical responsibilities towards the safety of participants and the safety of a study intervention under clinical investigation are met.

The sponsor has a legal responsibility to notify both the local regulatory authority and other regulatory agencies about the safety of a study intervention under clinical investigation. The sponsor will comply with country-specific regulatory requirements relating to safety reporting to the regulatory authority, institutional review boards (IRBs)/ethics committees (ECs), and investigators.

Investigator safety reports must be prepared for suspected unexpected serious adverse reactions (SUSARs) according to local regulatory requirements and sponsor policy and forwarded to investigators as necessary.

An investigator who receives an investigator safety report describing an SAE or other specific safety information (eg, summary or listing of SAEs) from the sponsor will review and then file it along with the investigator's brochure and will notify the IRB/EC, if appropriate according to local requirements.

